
### **Resting State Connectivity (Baseline and Week 32).**

Before treatment begins and at the 6 month follow-up appointment (week 32), a 10 minute resting state scan will be collected to derive measures of functional connectivity in the left and right executive control networks (LECN/RECN) following our previously published procedures (Weiland et al., 2014). These networks will be identified using functionally defined ROIs/nodes. The nodes for the LECN include: dorsolateral prefrontal cortex (DLPFC), left middle/superior frontal gyrus (MFG), left superior parietal gyrus/angular gyrus (PAR), left inferior/middle temporal gyri (TL), right crus I/crus II/Lobule VI (CE), and left thalamus (TH). The RECN nodes include: right DLPFC, right MFG, right PAR, right medial superior frontal gyrus (mSFG), left CE, and right caudate (CU). Functional connections between nodes, each pairwise correlation defined as an edge, will be calculated and used to create a correlation matrix between the time-series of all nodes within each network for each subject. A Fisher r-to-z transformation will be applied to r-values to yield z-scores. Connectivity strength as a primary global measure of connectivity for each network will be calculated as the mean of all pairwise

correlations between nodes within each network as well as other graph theory metrics (e.g., degree, efficiency, centrality). The framewise displacement (FD) for each subject will be calculated across the entire resting state run from the image motion parameter and used a covariate in the analyses.

### ***Blood Collection and DNA Methylation:***

#### **DNA Collection, Extraction, Storage, and Sequencing (Baseline, Week 4, 8, 20, 32).**

We will retain an aliquot of whole blood (approximately 10 mL) for DNA extraction. After extraction, DNA will be quantified and stored at -80° for future analysis. DNA will be collected at baseline, 4, 8, 20, 32 weeks so that we can monitor epigenetic changes over time.

#### **Bisulfite Sequencing / Estimation of Methylation.**

Bisulfite specific PCR primers will be designed using MethPrimer primer design software freely available at <http://www.urogene.org/methprimer/>. PCR amplification will use Accuprime™ *Taq* DNA Polymerase High Fidelity (Life Technologies™) in 50 ul reactions according to the manufacturer's instructions using 20 ng of converted genomic DNA with a final forward and reverse primer concentration of 200 nm each. PCR products will be purified using DNA Clean and Concentrator™-5 (Zymo Research) and quantified. Dual indexed libraries will be prepared using Illumina Nextera XT DNA Sample Preparation kit. Denatured and diluted libraries will be sequenced on the Illumina MiSeq benchtop sequencer with the sequencing by-synthesis technology per manufacturer's protocol. Data will be demultiplexed on the MiSeq instrument automatically, and zipped FASTQ files will be generated per sample, per read. Data will be accessed either in the run analysis folder locally on the instrument, or through BaseSpace beta. Custom scripts then determine the ration of methylation at each CpG in the amplicon. Average methylation across the CpGs identified in of our preliminary data will be used as the primary methylation measure in the analyses below.

### ***Blood Draw Collection and LPS Stimulation:***

#### **Blood Levels of Cytokines (Baseline, Week 4, 8, 20, 32).**

As noted in the background and in our description of our preliminary studies, we expect that MBRP will reduce biomarkers related to inflammation during the course of treatment and it is hypothesized that changes in inflammation will mediate the effects of MBRP on changes in connectivity in the brain, neurocognition, and drinking outcomes. Blood samples drawn at each assessment (baseline, 4, 8, 20, 32 weeks) will be assayed for IFNg, IL-1a, IL-1b, IL-6, IL-2, IL-4, IL-8, IL-10, IL-12, and TNF. Previous studies in animals (Mayfield et al., 2013) and humans (Bala et al., 2014), as well as our own preliminary data, suggest that cytokine activation is associated with the pathophysiology of AUDs. This is the same assay used in our preliminary studies.

#### **Liver Function Panel Tests (Baseline, Week 8, 20, 32).**

As stated in the study background, LPS-induced pro-inflammatory cascades span the brain, gut, and liver (Fernandez-Lizarbe, Pascual, & Guerri, 2009). Additionally, enzyme levels detected in a liver function panel (LFT) can indicate possible liver damage and cirrhosis cause by alcohol abuse (Bellentani et al., 1997). We expect to see changes in liver function tests as a result of decreased alcohol consumption and pro-inflammatory markers associated with RP and MBRP therapy. The LFT will also provide an additional objective measure of alcohol consumption to supplement the self-report measures we will collect. To detect differences pre and post-treatment as well as differences between

RP and MBRP treatment groups, we will have a liver function panel test performed on a 2mL sample of each participant's blood collected at baseline, 4, 8, 20, and 32 weeks. Liver function panels will be performed by Boulder Community Hospital Reference Lab.

### **Lipopolysaccharide (LPS)-PBMC challenge.**

We also expect MBRP to impact the responses of blood monocyte cells to an LPS challenge. This may represent a more accurate test of the effects of the treatment, since LPS stimulation of PBMCs simulates the TLR4 inflammation cascade that putatively mediates the neuroinflammatory effects of alcohol. To that end, 40 ml of whole blood will be drawn at each assessment point. Peripheral blood mononuclear cells (PBMC) will be separated using density gradient centrifugation. Cells will be counted and viability assessed using trypan blue exclusion. PBMCs will be exposed to LPS (0, 0.1, 1, 10 and 100 ng/ml) for 20h in a 96 well v-bottom plate. Protein levels of cytokines and chemokines (IL1, TNF, IL6, IL4, IL10, IFNg, MIP-1a) will be measured in supernatant using a multiplex ELISA assay (Aushon Biosystems, Billerica MA). mRNA levels of the same cytokines and chemokines will be measured in cell lysates using real-time PCR. We have successfully performed the PMBC isolation and LPS challenge in other projects.

### ***Gut Microbiome Sample Collection and Microbial DNA Extraction:***

#### **Fecal Sample Collection, Storage, Extraction, and Sequencing (Baseline, Week 8)**

We expect to see changes in both the number and diversity of microbiota populations found in the gut as a result of treatment and reduced alcohol consumption. Because inflammation, liver function, and the gut microbiome are heavily intertwined, we will examine the relationship between changes in the gut microbiome with changes in inflammatory biomarkers in the blood (cytokines and blood monocyte cell response to LPS challenge) and liver function as a result of both RP and MBRP therapy. Fecal samples will be collected from participants using at-home kits and then stored at -80°. Microbial DNA will be extracted from fecal samples and then analyzed to determine how many and which bacterial species are present in the gut. Gut microbiome data will be collected at baseline and 8 weeks so that we can monitor changes in number and diversity of microbial DNA pre and post-intervention.

Due to the COVID-19 situation we are collecting remote data only and will return to our original protocol when it is safe to do so. The remote RESEARCH STUDY DESIGN will be as follows:

Because of the remote nature of the study, we will not be collecting the data mentioned above: MRI data, microbiome samples, or blood data.

We will be administering the parts of this study that can be done remotely through contact with a research assistant: All therapy sessions (mentioned above), and the Validating Self-report Measures listed directly below.

Additionally, due to the necessity of the remote nature attributable to COVID: All participants will need access to the internet whether by computer, smartphone, or other device such that they can complete this study. A research assistant will send unique links to participants that they will simply click on in order to participate, applications such as: Zoom (an internet application that allows us to see

and talk with the participant), Qualtrics and REDCap (online survey platforms), and DocuSign (an internet application that allows us to send forms for signatures).

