Subjects will then complete baseline questionnaires related to their demographics, history of drinking, smoking and drug use, and alcohol craving (measures listed below). Also, subjects will take six neurocognitive tests using the NIH toolbox application, which will assess their cognitive function in terms of memory and attention. If not eligible for the MRI, subjects will be randomly assigned to receive MBRP or RP for the next 8 weeks at the end of their baseline session and will also be given their microbiome sample collection kits at the end of the session. They will return the sample kits at their next scheduled session. Subjects will be compensated \$30 for completion of the baseline appointment.

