After the scan, a research assistant will escort the participants back to the changing room where their belongings are locked. Subjects in this group will be given their MBRP or RP condition assignment after the scan is complete in order to minimize any expectancy effects that may occur as a result of knowing their condition assignment before all pre-treatment measures have been taken. Subjects will be compensated \$30 for completion of the MRI scan I appointment.

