### Resting State Connectivity

- For this sequence, participants will be asked to just lie still and stay awake. No other actions on their behalf are needed. This resting state scan will be collected to derive measures of functional connectivity in the left and right executive control networks (LECN/RECN) following our previously published procedures (Weiland et al., 2014). These networks will be identified using functionally defined ROIs/nodes. The nodes for the LECN include:

*10 minutes*

dorsolateral prefrontal cortex (DLPFC), left middle/superior frontal gyrus (MFG), left superior parietal gyrus/angular gyrus (PAR), left inferior/middle temporal gyri (TL), right crus I/crus II/Lobule VI (CE), and left thalamus (TH). The RECN nodes include: right DLPFC, right MFG, right PAR, right medial superior frontal gyrus (mSFG), left CE, and right caudate (CU). Functional connections between nodes, each pairwise correlation defined as an edge, will be calculated and used to create a correlation matrix between the time-series of all nodes within each network for each subject. A Fisher r-to-z transformation will be applied to r-values to yield z-scores. Connectivity strength as a primary global measure of connectivity for each network will be calculated as the mean of all pairwise correlations between nodes within each network as well as other graph theory metrics (e.g., degree, efficiency, centrality). The framewise displacement (FD) for each subject will be calculated across the entire resting state run from the image motion parameter and used a covariate in the analyses.

Visit/Session	Procedures/Tools	Location	Time to Complete
Baseline Session	
 
• Informed consent; Study orientation; BAC test; Urine drug test; Questionnaires; Neurocognitive
 
	CINC	2 hours and 30 minutes

	tests; Blood draw; receive microbiome kit		
MRI Scan I	
 
• BAC test; Pregnancy test; MRI
 
	CINC	1 hour
Goal-setting Session	
 
• BAC test; a goal setting session with a therapist to discuss drinking reduction goals for the next 8 weeks; return microbiome kit
 
	CINC	1 hour

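### The baseline stool sample of in-person participants not eligible for MRI is produced after random assignment, and for scanned participants the plan does not fix whether it comes before or after they learn their arm

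*Combined protocol and SAP*

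**What the plan says.** Section IV, on fecal sample collection, sets two stool samples: "Gut microbiome data will be collected at baseline and 8 weeks so that we can monitor changes in number and diversity of microbial DNA". It also says how they are obtained: "Fecal samples will be collected from participants using at-home kits".

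Section XI, Baseline Session, sets the order for people who cannot be scanned: "subjects will be randomly assigned to receive MBRP or RP for the next 8 weeks at the end of their baseline session". The same sentence has them given the stool kit at the end of that session, and the next one reads: "They will return the sample kits at their next scheduled session". Earlier in the same section the kit is to come back at the first scheduled session.

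Section XI, MRI Scan I, treats scanned participants differently: "Subjects in this group will be given their MBRP or RP condition assignment after the scan is complete in order to minimize any expectancy effects". The expectancy effects it has in mind are those that come from "knowing their condition assignment before all pre-treatment measures have been taken".

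The visit table in Section XI lists goal-setting after MRI Scan I, with this content: "discuss drinking reduction goals for the next 8 weeks; return microbiome kit".

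Hypothesis 5 (Section I) and the Exploratory Aim 1 analysis (Data Analysis Plan) compare the arms on gut microbiota before treatment as well as after it.

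**The concern.** A baseline measure is protected by randomisation only if it is taken before anything can depend on the arm. If the sample truly precedes assignment, any arm difference in it is chance. If it follows assignment, and the participant knows the arm, the difference may also reflect early changes in drinking or diet made in response. The two explanations cannot then be separated.

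This matters here because the pre-treatment arm comparison is itself a stated analysis, and because the plan intends to relate changes in the microbiome to changes in inflammation and liver function. Both use the baseline sample.

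**Working it through.** No arithmetic applies to the timing; the check is to set the steps of each pathway side by side.

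| Step | Not eligible for MRI | Scanned |
|---|---|---|
| Blood, urine and breath tests, questionnaires, neurocognitive tasks | Baseline session | Baseline session |
| Kit handed out | End of baseline session | End of baseline session |
| Assignment | End of baseline session | Made at an unstated time; told after the scan |
| Stool produced | At home, after the baseline session | At home, after the baseline session; before or after the scan not fixed |
| Kit returned | Next session; goal-setting in the table | First scheduled session in the text; goal-setting in the table |
| 8-week programme starts | After goal-setting | After goal-setting |

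**Not eligible for MRI.** Kit and assignment are given at the same visit and the sample is made later at home. Whichever of the two comes first at the end of that visit, the sample follows assignment. The wording at this point is that they are assigned, not that they are told. Disclosure at that visit is an inference, drawn from the contrast with the MRI section, which does describe participants being given their assignment. It is probable but not written.

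**Scanned.** If the first scheduled session means the scan visit, the sample precedes disclosure. If the kit is returned at goal-setting, the sample may be made either before the scan or between the scan and goal-setting, and in the second case it follows disclosure. The documents do not settle which.

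**Other baseline measures.** In the order given for the baseline session, all the laboratory measures are taken before the assignment that closes the visit. Stool is the only pre-treatment measure shown to fall after it.

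**Which analyses use the sample.** The Exploratory Aim 1 plan fits regressions of microbiome values on age, gender, fruit and vegetable intake and arm, both before and after treatment. It specifies no baseline adjustment or change score for the arm comparison. The week-8 regression therefore does not use the baseline sample. The pre-treatment regression and the exploratory work on changes do.

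**Size.** The interval between assignment and sample is not stated. Neither is the number of in-person participants who cannot be scanned. Section XIII expects about 150 metagenomes in all but does not split them by visit or by scan eligibility. The affected share cannot be computed.

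**The case against.** The strongest reply is that little is lost. Goal-setting precedes the programme, so the sample is still taken before therapy. The aim is exploratory, and the week-8 comparison stands without the baseline sample. In remote mode no stool is collected, so the question does not arise. All of this is correct and limits the point.

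A reader might infer that the protocol breaks its own rule for people who cannot be scanned. It does not: the timing in the MRI section is written for the scanned group only. What fails is the rationale, which applies equally to a stool sample and is not carried over.

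A reader might also infer that assigning a visit before goal-setting dilutes the heavy-drinking-days comparison, because people who never start stay in the all-randomised analysis. The documents do not support that as a defect or give it a size. Analysing everyone randomised is the planned intent-to-treat rule and does not follow from the kit timing. People who do not come back supply no follow-up drinking data and fall within the planned 20% attrition (180 / (1 - 0.20) = 225, against about 226 to be recruited). Dilution would need never-starters who are still followed up, and no rate for them is given. At most, later assignment might also reduce the number randomised who never start, by an amount that cannot be estimated from the documents.

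**Conclusion.** The point holds as a minor one, confined to Exploratory Aim 1. For in-person participants not eligible for MRI, the written sequence puts every baseline stool sample after assignment. That it also follows disclosure is a probable inference. For scanned participants the order is unresolved, because the kit-return wording conflicts between the baseline text and the visit table.

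As planned, an arm difference in the pre-treatment sample could not be read as a clean baseline comparison, and the change analyses could carry behaviour changed after assignment. The direction and amount cannot be stated. It would go too far to say that the week-8 microbiome comparison or the primary outcome is compromised.

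**What to change.** In Section XI (Baseline Session, MRI Scan I and the visit table), state one kit-return point. For all in-person participants, make and disclose the assignment at the start of the goal-setting session, after the stool kit has been handed in. Add that a kit not returned by then is recorded as a missing baseline sample and does not delay assignment. The remote procedures need no change for this purpose.

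The cost is protocol wording, with no extra visit, measurement or staff. The one small downside is that the goal-setting slot must be booked before the arm is known. Section IV has therapists cross-trained and delivering both conditions equally, so this is workable.

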### ***Validating Self-report Measures:***

#### **Biochemical Outcome Measures (Baseline, Week 8, 20, 32).**

Following the procedures and recommendations outlined in a report on biochemical verification of abstinence, tests of plasma **%CDT and GGT** will be used as an unbiased, biological outcome variable that will be used to validate self-report measures (Anton, Lieber, & Tabakoff, 2002) (Martínez-Raga et al., 2002).

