#### **Specific Aim 1 - Detecting Treatment Effects on Drinking Outcomes.**

The effect of the treatment on alcohol use outcomes (HYPOTHESIS 1) will be analyzed with a 2 (**Treatment:** 8 weeks of MBRP vs. 8 weeks of RP) x 5 (**Time:** Baseline, 4, 8, 20, 32 weeks) mixed general linear model with Heavy Drinking Days (HDD) as the primary outcome variable. We will also examine drinks per drinking day, ICS score, and liver function tests as dependent measures in each of 2 additional models, respectively. In the main analysis with HDD, a significant overall test of the treatment X time interaction will be followed by planned contrasts within the mixed model that allow us to test the superiority of MBRP over RP at the 8, 20, and 32 week follow-up points specifically. The FIML estimation procedure implemented in these analyses will allow us to utilize an “intent to treat” approach such that all subjects who are randomized will be included in the analyses (Schafer & Graham, 2002). It may be that the treatments are equally effective on drinking outcomes, and thus we will not see a direct effect of treatment on outcomes. Even in this case, it is possible that the mechanisms through which the treatments had their impact may differ. Thus, tests of Specific Aims 2 and 3 are still important and warranted.

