## **VIII. COMPENSATION**

---

We estimate that the completion of assessments and procedures across the duration of the trial, including therapy sessions, will total approximately 16 hours of time (an additional 2 hours for MRI). To compensate subjects for their time and travel costs, subjects who will not be scanning will be paid a maximum of \$280 if they complete all therapy sessions and appointments and those subjects who will be scanned will be paid a maximum of \$340. As a breakdown for compensation participants will be given:

- \$30 for completing the Baseline Session (an additional \$30 will be given to participants who undergo the first MRI scan)
- \$30 at the Intermediate Session (week 4)
- \$30 for completing the End of Treatment Session (week 8)
- \$15 for each therapy session they attended (week 1-3 and 5-7) (\$90 total; will be given in total to participants at week 8)
- \$50 for completing the full week 20 follow-up (\$30 will be given for completing surveys, whether completed in our laboratory or remotely; \$20 will be given for blood sample collection, which can only occur in our laboratory)
- \$50 for completing self-report measures for the week 32 follow-up (\$30 will be given for completing surveys, whether completed in our laboratory or remotely; \$20 will be given for blood sample collection, which can only occur in our laboratory; an additional \$30 will be given to participants who undergo the second MRI scan)

Due to the COVID-19 situation we are collecting remote data only and will return to our original protocol when it is safe to do so, the remote COMPENSATION will be as follows:

Compensation (via Amazon gift cards) for each study appointment goes as follows:

- Baseline session: \$30
- Therapy sessions (weeks 1-3, 5-7): \$15 per session (\$90 total given at week 8)
- Intermediate session (week 4): \$30
- End of treatment session (week 8): \$30
- Follow-up session I (week 20): \$50 for surveys
- Follow-up session II (week 32): \$50 for surveys

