### **Baseline Session**

After arriving at the lab, qualified participants will (1) complete an informed consent form, and then (at either the same session or a separate session), participants will (2) complete a breath alcohol test, (3) complete a urine toxicology screen, (4) provide a blood sample for assays of peripheral inflammatory markers and DNA methylation, (5) fill out the baseline questionnaires, (6) and take several neurocognitive tasks. Participants will also be given a gut microbiome sample collection kit at the end of the session and will return it to their first scheduled session (7).

Subjects will be breathalyzed before every session starts, including all therapy sessions. Any subject that has a positive BAL or who reports drinking will be rescheduled for that appointment. A participant who blows a BAC over 0.00 will be given one chance to reschedule his/her appointment for the next day. If s/he comes in the next day with a breath alcohol greater than 0.00 then this session will be counted as “missed.” If a subject accumulates more than one “missed” session, they will be automatically dropped from the study on the grounds that they failed to follow explicit study directions properly. Participants will not receive compensation if a session is terminated due to failure to follow the abstinence instructions. They will be informed of this contingency during the phone screen, consent visit and is stated the consent form.

A urine toxicology screen will be administered to insure that subjects have not recently used illicit drugs including, sedatives, opiates, cocaine, or amphetamines.

A member of our research team who has completed a certified training in phlebotomy will collect the blood sample. The blood draw procedures will involve collecting venous blood (40 ml) venipuncture of a peripheral arm vein using standard, sterile phlebotomy techniques. The samples will be tested for cytokine levels and epigenetics using equipment at the CINC.

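### The remote (COVID-19) design promises a plasma check on self-report while excluding blood, and the HDD model has no term for delivery mode

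*Combined protocol and SAP*

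**What the plan says.** The remote design is set out at the end of the fecal-sample subsection of section IV. It is temporary: "we are collecting remote data only and will return to our original protocol when it is safe to do so". One trial therefore holds participants treated in person and participants treated by telehealth.

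On data, that text says "we will not be collecting the data mentioned above: MRI data, microbiome samples, or blood data". It then lists what remote participants will receive: "All therapy sessions (mentioned above), and the Validating Self-report Measures listed directly below". The next heading is Validating Self-report Measures. Its only entry, Biochemical Outcome Measures (baseline, weeks 8, 20 and 32), begins "Following the procedures and recommendations outlined in a report on biochemical verification of abstinence, tests of plasma" and names %CDT and GGT, which "will be used as an unbiased, biological outcome variable that will be used to validate self-report measures".

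Section VIII describes "blood sample collection, which can only occur in our laboratory". For the in-person design, section XI says "Subjects will be breathalyzed before every session starts, including all therapy sessions". The remote visit table in section XI lists consent and orientation, goal-setting, therapy and questionnaires, with no blood draw and no breath test.

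The Aim 1 analysis is a treatment × time "mixed general linear model with Heavy Drinking Days (HDD) as the primary outcome variable", fitted to all randomised subjects. The only route for other covariates is the pretest-equivalence rule, which adds baseline measures found unequal between arms. Delivery mode is not listed as a baseline measure.

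**The concern.** There are two separate issues.

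First, the remote text contradicts itself. It excludes blood and then assigns remote participants a set of measures consisting only of plasma tests. HDD is self-reported on the Timeline Follow Back, so a reader could believe the primary outcome has a biochemical check at remote visits when none is possible.

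Second, the modes differ in delivery, in blood sampling and in listed breath testing, and the HDD model has nothing to represent this. If mode is related to the course of reported drinking, leaving it out adds residual variance. If the MBRP effect were weaker by telehealth, or if one arm under-reported more at remote visits, the pooled contrast would absorb it and no planned analysis would show it.

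**Working it through.** **1. Cross-reference.** Remote text: no blood. Same text: the measures under the next heading are given. That heading: plasma %CDT and GGT only. Section VIII: blood only in the laboratory. Remote visit table: no sample. The second statement cannot be carried out as written.

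**2. The plan's power figure.** Inputs from Power for Specific Aim 1: 180 completers, 5 assessments, f = .10, correlation .50, alpha .05. For the treatment × time F test, λ = N·m·f²/(1−ρ) = 180 × 5 × .01/.5 = 18, with 4 and 712 df. Power is .942, which agrees with the stated value of well over .90. The recruitment figure also reproduces: 180/.8 = 225, against about 226.

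**3. Does omitting mode harm the test?** A null simulation used 90 per arm, 4,000 trials per setting, remote shares of 10, 30 and 50%, and an assumed .5 SD mode shift at every post-baseline visit. Type I error was .045 to .054 without the mode term and .047 to .055 with it. The simulation standard error is √(.05 × .95/4000) = .0034, so all values are consistent with .05.

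**4. Precision forgone.** With remote share p and mode difference δ in SD units, mode explains p(1−p)δ²/(1 + p(1−p)δ²) of the variance. For assumed p of .2 to .5 and δ of .3 to .5, this runs from .0144/1.0144 = 1.4% to .0625/1.0625 = 5.9%.

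**5. Cost of adding the terms.** Mode (1) plus mode × time (4) is five parameters. The error df for the interaction test fall from 712 to 708, and power stays at .942.

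**6. What could go unseen (all assumed).** If the treatment effect were zero in remote participants, pooled λ = 18(1−p)². The three-way test of that difference has λ = 18p(1−p). In-person power uses the in-person completers alone.

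| Remote share | Pooled power, zero remote effect | Three-way power | In-person n | In-person power |
|---|---|---|---|---|
| 10% | .88 | .15 | 162 | .91 |
| 20% | .78 | .23 | 144 | .87 |
| 30% | .65 | .30 | 126 | .82 |
| 40% | .50 | .34 | 108 | .75 |
| 50% | .36 | .36 | 90 | .66 |

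If the arms differed in remote misreporting, the shift in the pooled contrast would be remote share × differential. For example, .25 × .2 SD = .05 SD, which is 25% of the d = .20 implied by f = .10. Across shares of 10 to 50% and differentials of .1 to .4 SD, the range is 5 to 100%. This shows the scale only; nothing in the documents says such a differential exists.

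**The case against.** The strongest reply is that the cross-reference is a slip. The questionnaires follow shortly after, and the remote procedures list only questionnaires, so the authors probably meant those. That is likely, but the questionnaires stand under a different heading (Measures and Assessments), and the text needs correcting on either reading.

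A reader might infer that validated and unvalidated HDD values are being mixed. The documents do not support that. HDD comes from the Timeline Follow Back for everyone, and no rule lets %CDT or GGT confirm, change or replace an HDD value. These tests are not scheduled at week 4, and the original design already allows survey-only follow-up at weeks 20 and 32. What differs between visits is whether a biochemical check is available, and missing blood results would be visible in the data.

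A reader might also infer that pooling biases the MBRP–RP comparison. Randomisation protects it, and step 3 agrees. Chance imbalance in mode between arms could be turned into a shift: with 113 per arm and 20 to 50% remote, 1.96√(2p(1−p)/113) gives ±.104 to ±.130. Multiplied by an assumed .3 to .5 SD, that is .03 to .065 SD. But this takes an extreme draw times an assumed effect, and the standard error already covers such variation. It is not bias.

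Nor do the documents say that remote recruitment uses social media exclusively, or that the in-person breath-test rule is withdrawn for remote participants. The remote text is silent on the latter.

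The remote share may also be small. The project timeline puts 200 of 226 enrolments in the first four years. If remote enrolment fell only in the fifth, the share would be 26/226 = 12%; slower accrual would raise it.

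**Conclusion.** Both facts hold: the remote text contradicts the heading it points to, and the HDD analysis has no delivery-mode term or sensitivity analysis. The consequence is minor. The randomised comparison stays valid and type I error stays near .05. The losses are some precision (1.4 to 5.9% of variance under the assumptions in step 4) and any view of whether the HDD result differs by mode or holds where a biochemical check exists. The actual size cannot be given, because the remote share, the mode effect and any arm-differential misreporting are all absent from the documents. No stated power or sample-size figure is disputed.

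**What to change.** 1. Reconcile the remote text in section IV with the Biochemical Outcome Measures entry, stating that no biochemical check on self-reported HDD is available at remote visits.

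2. In the Aim 1 analysis, add delivery mode at randomisation (in person or remote) and mode × time as fixed effects. This costs five parameters, with power unchanged at about .94. The variable is known at randomisation for every participant.

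3. As a descriptive sensitivity analysis, report the week 8, 20 and 32 MBRP–RP contrasts by mode from a separate model that also has treatment × mode and treatment × mode × time (1 + 4 = five more parameters). The model in item 2 cannot supply these, because it forces one treatment contrast on both modes.

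4. Record a per-visit flag for whether a %CDT/GGT sample was obtained, and repeat the HDD analysis on flagged visits only. Mode at randomisation is not a substitute, since participants randomised in person may have survey-only follow-up. Week 4 drops out by schedule, and sample availability depends on attendance after randomisation, so this too is descriptive.

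The cost is analysis-plan wording and one data flag. The downside is imprecise by-mode estimates: three-way power of about .15 to .36 for an assumed 10 to 50% remote share, so they cannot be confirmatory.
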